3.5 Measures taken to minimize/avoid bias

3.5.1 Randomization

Patients will be allocated to the two treatments, i.e., oral prednisolone and placebo, in a ratio of 1:1 by central randomization within each age group.

The randomization procedure will not consider the sex of the patients, since no sex-specific responses to prednisolone therapy have been reported yet and are not expected. The randomization list will be generated by the IZKS Mainz using a pseudo-random number generator to ensure that the resulting treatment allocation will be both reproducible and non-predictable.

During inpatient treatment each patient to be included will receive the next consecutive random/patient number from a block of randomization numbers. Study medication will be packed and blinded according to the random list. Each patient medication box will be sent together with the sealed unblinding codes (i.e. envelopes) to the sites. The investigator has to take care that each patient will be provided with the study medication box bearing the correct randomization number.

The randomization list is to be kept confidential and is only accessible to authorized personnel until the code is broken. At the end of the trial, any emergency opening of the envelopes will be controlled after collecting the explanations for unblinding and checking the unused treatment units. The code will be broken regularly only at the end of the study after freezing the statistics database (by checking the data, recording any protocol violations etc.) allowing the collected data to be analyzed.

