STATISTICAL ANALYSIS	
Efficacy: The primary analysis variable is the improvement in FVC (difference after 6 months and baseline). The 6 months and baseline FVC values will be given in percent deviation from the norm values tabulated by Quanjer PH., et al. 2013. A difference between the changes in placebo and active treatment is considered not significant if FVC differences are < 7%. The working hypothesis of the study is that the placebo intervention is not inferior to the prednisolone intervention.
 
Description of the primary efficacy analysis and population: The improvement in FVC will be compared between groups within an analysis of covariance (ANCOVA). Treatment will serve as a fixed factor and the baseline FVC value as a covariate. The primary analysis population will consist of all randomized patients without any major protocol violations. The two-sided 90% confidence interval for the treatment difference will be calculated. Sensitivity analyses will be performed by analysing the same analysis model for all randomized patients. Additionally, the primary parameter will be analysed by ANCOVA with additional terms for sex and height. Centre effects will be explored by descriptive statistics.
 
Safety: Adverse events will be coded by MedDRA and analysed by descriptive methods. Laboratory values will be displayed by sample characteristics over time and compared between groups by exploratory p-values.
 
Secondary endpoint(s): Secondary endpoints will be displayed by descriptive statistics and compared between groups by exploratory p-values.

SAMPLE SIZE	
To be assessed for eligibility: (n=60) To be allocated to trial: (n=45) To be analyzed: (n=40)

TRIAL DURATION	
First patient in to last patient out (months): 24 Duration of the entire trial (months): 27 Recruitment period (months): 18

PARTICIPATING CENTERS	
About 40 trial sites are planned to participate

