3.2 Number of subjects

It is planned to assess 60 subjects for eligibility, to allocate 45 subjects to the trial and to analyse 40 subjects.

Recruitment and treatment of subjects is expected to be performed in > 40 trial centers.

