7.1 Sample size

Power calculations were based on a one sided level of significance of alpha=0.05. Regulatory guidelines suggest the use of a two-sided level of significance. However, it is extremely improbable that in the time frame of the study the prednisolone arm will be significantly worse than the placebo arm. Power calculations were performed by means of a t-test with a correlation to the baseline value of 0.4. With 40 patients evaluable per protocol the study will have a power of 58% to detect non-inferiority of the placebo arm versus the prednisolone arm with a non-inferiority bound of 7%. The power calculations were done by SAS, Version 9.2.

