7.3 Efficacy analyses

Efficacy:

The analyses will be specified more detailed in the statistical analysis plan (SAP). Descriptive statistics of qualitative data will consist of absolute and relative frequencies. For quantitative data the number of observations, mean, standard deviation, minimum and maximum will be presented.

The primary population for the analyses of efficacy is the randomized Population without major protocol violations.

7.3.1 *Definition and analysis of primary endpoint*

The primary analysis variable is the improvement in FVC (difference after 6 months and baseline). The 6 months and baseline FVC values will be given in percent deviation from the norm values tabulated by Quanjer PH., et al. 2013.

A difference between the changes in placebo and active treatment is considered not significant if FVC differences are < 7%. The working hypothesis of the study is that the placebo is not inferior to the prednisolone intervention.

The improvement in FVC will be compared between groups within an analysis of covariance (ANCOVA). Treatment will serve as a fixed factor and the baseline FVC value as a covariate. The primary analysis population will consist of all randomized patients without any major protocol violations. The two-sided 90% confidence interval for the treatment difference will be calculated. Sensitivity analyses will be performed by analyzing the same analysis model for all randomized patients. Additionally, the primary parameter will be analyzed by ANCOVA with additional terms for sex and height. Center effects will be explored by descriptive statistics. Missing values will not be replaced.

If appropriate, a Bayesian analysis with a suited prior distribution will be considered. This will be specified in the statistical analysis plan (SAP).

7.3.2 *Analysis of secondary endpoints*

All analysis of secondary endpoint will be interpreted purely exploratory. Descriptive statistics will be displayed for all

- Response according to the primary analysis variable: Each patient will be classified as a responder or non-responder. A patient is considered as a responder, if the FVC value after 6 months is more than or equal to 93% of the norm values tabulated by Quanjer PH., et al. 2013 and if the patient did not take any glucocorticoid rescue medication. Responders will be analysed by a Chi-Square Test.

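### Randomization is stratified by age group, but the primary ANCOVA leaves age group out; adding it is nearly free and gains about 0 to 4 points of power at an assumed partial R² of 0 to 0.10

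*Protocol*

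**What the plan says.** - **Allocation (section 3.5.1).** Patients are assigned "in a ratio of 1:1 by central randomization within each age group". The same section says that sex is not considered in the randomization. The protocol does not state the number or limits of the age groups.
- **Primary model (synopsis, Statistical analysis; section 7.3.1).** "Treatment will serve as a fixed factor and the baseline FVC value as a covariate". No other term is named.
- **Sensitivity analysis (section 7.3.1).** "Sensitivity analyses will be performed by analyzing the same analysis model for all randomized patients". It therefore has no age-group term either.
- **Further model (section 7.3.1).** Two covariates are brought in, neither of them age group: "Additionally, the primary parameter will be analyzed by ANCOVA with additional terms for sex and height".
- **Analysis set (section 7.3.1).** "The primary analysis population will consist of all randomized patients without any major protocol violations". Section 3.2 plans "to allocate 45 subjects to the trial and to analyse 40 subjects".
- **Scale (section 7.3.1).** "FVC values will be given in percent deviation from the norm values".
- **Power (section 7.1).** "With 40 patients evaluable per protocol the study will have a power of 58" per cent, with a margin of 7% and a one-sided alpha of 0.05.

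**The concern.** A factor used to stratify randomization normally belongs in the primary model. Stratifying balances the arms on age group, but the model gets the resulting gain in precision only if it contains the factor. Without it, any variation between age groups stays in the residual, the standard error is too large on average, and the test is slightly conservative.

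There is a second risk. The primary set removes patients after randomization, so balance within age groups is not guaranteed among those analysed. If losses gather in one arm of one age group, and age group is prognostic, the estimate from the stated model is biased. In a non-inferiority comparison, a bias in favour of placebo raises the chance of wrongly declaring placebo non-inferior.

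This is not a detail left to the SAP, because the protocol itself fixes the model terms. It gives a term to sex, which was not used in randomization, and none to age group, which was.

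**Working it through.** **Inputs from the protocol.** 40 evaluable patients, 1:1 allocation (20 per arm), one-sided alpha 0.05 (the two-sided 90% interval), margin 7, power 58%; 45 allocated.

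**Assumptions, since the protocol gives no value.** True difference 0; two age strata; partial R² of age group, given baseline FVC, between 0 and 0.10.

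**Step 1: the stated power.** No SD or true difference is given, so 58% cannot be reproduced independently; it can only be solved backwards. With treatment and baseline in the model, df = 40 − 3 = 37. A noncentral t power of 58% needs a noncentrality of 1.881. From 1.881 = 7 / (SD × √(2/20)), SD = 7 / (1.881 × 0.3162) = 11.77.

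**Step 2: cost of the term if age group is not prognostic.** With noncentrality held at 1.881, power is 58.0% at 37 df, 57.96% at 36 df, 57.84% at 33 df and 57.5% at 27 df.

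**Step 3: gain if it is prognostic.** The residual SD becomes 11.77 × √(1 − R²). With one df spent, power is 57.96%, 59.83% and 61.82% at R² 0, 0.05 and 0.10. With three df spent it is 57.88%, 59.74% and 61.73%. The change from 58.0% is therefore about −0.1 to +3.8 points.

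**Step 4: simulation with exclusions.** 45 patients in strata of 22 and 23, 40 analysed, 40,000 trials per cell. Non-inferiority is declared if the lower 90% limit lies above −7. Power is taken at a true difference of 0 and error at −7 (placebo minus prednisolone). Entries are percentages at R² 0 / 0.05 / 0.10; splits are placebo:prednisolone.

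| Exclusions | Measure | Without age group | With age group |
|---|---|---|---|
| At random | Power | 56.8 / 56.7 / 56.8 | 56.6 / 58.1 / 60.5 |
| At random | Error | 4.89 / 4.55 / 4.33 | 4.87 / 5.01 / 5.01 |
| Lower-gain stratum, 3:2 | Error | 5.04 / 4.92 / 4.85 | 5.04 / 4.92 / 5.06 |
| Lower-gain stratum, 4:1 | Error | 5.06 / 5.87 / 5.98 | 5.11 / 5.04 / 4.99 |
| Lower-gain stratum, 5:0 | Error | 5.07 / 6.94 / 7.68 | 5.01 / 5.08 / 5.01 |
| Higher-gain stratum, 5:0 | Power | 56.1 / 49.0 / 45.3 | 55.2 / 57.7 / 59.1 |

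With random exclusions the gain is −0.2, +1.4 and +3.7 points, in line with Step 3. At R² 0.10 the mean 90% interval is 12.7 points wide without the term and 12.0 with it.

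A smaller case has 44 patients in two strata of 22, with four placebo patients lost from the lower-gain stratum. At R² 0.02, 0.05 and 0.10 the error is 6.01%, 6.33% and 6.54% without the term, against 5.11%, 4.93% and 4.89% with it.

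**Step 5: check on the bias.** With two equal strata, the difference between them is 2 × SD × √R²: 5.26 points at R² 0.05 and 7.44 at 0.10. Losing four of 11 placebo patients in the lower-gain stratum leaves 7 and 11, so the higher-gain share rises from 0.50 to 11/18 = 0.611. The bias towards placebo is 0.111 × 5.26 = 0.58 and 0.111 × 7.44 = 0.83 points. A separate simulation of this case gave 0.56 and 0.80 without the term and about 0.01 with it.

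**The case against.** In the ordinary case the stated model is valid: with random exclusions its error is at or below 5%, so only efficiency is lost. The R² range has no source in the protocol. FVC is referenced to norm values and baseline FVC is already a covariate, so the remaining age effect may be near zero, and then the term brings no gain or a small loss (56.1% to 55.2% in the 5:0 case at R² 0). All of this stands.

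The error inflation needs an extreme pattern. If exclusions are unrelated to arm and age group, the chance that all five fall in one cell, with cells of 11, 11, 11 and 12, is (3 × 462 + 792) / 1,221,759, about 0.18%. A 3:2 split shows no inflation. This stands too, although losses need not be unrelated to arm: sections 3.5.2 and 3.6.3 withdraw patients after unblinding and allow withdrawal on deterioration.

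The term corrects imbalance in age group only. The simulations make exclusion independent of outcome within age group; exclusions that depend on outcome or treatment in other ways would still bias a per-protocol comparison.

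Height, in the additional model, may partly stand in for age in patients aged 6 to 25, but only in a supplementary analysis.

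Finally, many small strata would raise the cost. If the term had to absorb chance imbalance, as under unstratified allocation, the change would be about −1.0 to +2.8 points with one df and −2.1 to +1.7 with two. Stratified allocation largely avoids this.

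These points limit the size of the benefit. None is a reason to leave out a factor that the design already uses.

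**Conclusion.** The concern holds. The protocol stratifies by age group and fixes a primary model without it, and neither the all-randomized analysis nor the additional model supplies it.

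The expected benefit is modest: about 0 to 4 points of power over R² 0 to 0.10 if exclusions are random. The protection against concentrated exclusions is larger, with error near 5% instead of about 6 to 8%, and power of 58 to 59% instead of 45 to 49%. It matters only if age group is prognostic and losses are strongly lopsided.

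All figures rest on an SD solved backwards from the stated power, a true difference of 0, two strata and an assumed R². The change is worth making because it costs almost nothing. It does not repair the low planned power.

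**What to change.** In the synopsis and section 7.3.1, make treatment and the age group used for randomization the fixed factors, with baseline FVC as the covariate. For example: *The model will contain treatment and the randomization age group as fixed factors, and baseline FVC as covariate.* The all-randomized sensitivity analysis then inherits the term. Keep sex and height as the additional analysis. The same term in the exploratory secondary ANCOVAs is optional. Stating the age groups next to the model would make the number of terms clear.

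The cost is the number of age groups minus one degrees of freedom. If age group has no effect, that is 0.04 points of power for two groups (58.0% to 57.96%) and 0.5 points for eleven (57.5% at 27 df), before any loss from unbalanced exclusions. No data collection or sample size changes. If the change counts as a major modification of the primary analysis, section 7 requires a protocol amendment as well as the SAP entry. It should be settled before the blind is broken.

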3.5.2 Blinding

Blinding will be achieved by providing the study-specific prednisolone and placebo tablets in blinded capsules.

In the case of a medical emergency requiring identification of the treatment taken by the patient, the investigator has the right to open the respective envelope, but every effort should be taken to avoid unblinding of patients except the information will be needed for the emergency treatment. Opened envelopes have to be signed, dated and the reason for unblinding has to be documented. The envelope has then to be filed in the patient notes and the sponsor and/or the responsible monitor has to be informed. Unblinded patients have to be withdrawn from the study. No other reason than an emergency may justify unblinding. After unblinding the investigator has also to note the date, time and reason in the source documents.

The unblinding codes are not to be opened by the investigator at the end of the trial.

3.6 Selection and withdrawal of subjects

No subject will be allowed to enrol in this trial more than once.

3.6.1 Inclusion criteria

Subjects meeting all of the following criteria will be considered for admission to the trial:

1. Newly or previously diagnosed but not appropriately treated EAA in children, adolescents and young adults, aged between 6 and 25 years. The diagnosis of EAA must be confirmed by independent review of the findings by an expert panel and must be based on the presence of at least 4 of the following findings:

- * History of appropriate allergen exposure
- * Restrictive lung function (FVC < 80% predicted for age and FVC/FEV1 < 1) testing, if appropriate for age (usually > 5 y)
- * Positive serum precipitins for bird/fungus exposed to (other allergens have rarely, if ever been demonstrated in children)
- * Lymphocytosis in BAL (> 20% of cells are lymphocytes)
- * HRCT showing the characteristic nodular, linear or reticular opacities, and ground glass pattern with increased attenuation.
- * Lung biopsy demonstrating lymphocytic alveolitis, bronchiolitis, and non-caseating histiocytic granulomatas.
- * Controlled allergen exposure followed by characteristic reaction, including fever, coughing, restriction on lung function, hypoxemia/desaturation at rest or with exercise

2. Unchanged inhaled steroids if on; if off, no plans to introduce them in the following 6 months

3. Agreement to home visit by independent study physician

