OBJECTIVE(S)	
Primary objective: To evaluate outcome of EAA at 6 months and compare medium term treatment with systemic steroids or placebo.
 
Secondary objectives: To evaluate the completeness and knowledge of standardized and pediatric allergen elimination in families with a child with EAA. To evaluate the treatment of EAA with systemic steroids compared to placebo at 3 months To evaluate the safety of the treatment of EAA with outpatient usage of systemic steroids compared to placebo

INTERVENTION(S)	
Experimental intervention: Placebo
 
Control intervention: Prednisolone
 
Duration of intervention per patient: 3 months
 
Follow-up per patient: 6 months

KEY INCLUSION AND EXCLUSION CRITERIA	
Key inclusion criteria:
 
 1. Newly or previously diagnosed but not appropriately treated EAA in children, adolescents and young adults (6 to 25 years). The diagnosis of EAA must be confirmed by independent review of the findings by an expert panel and must be based on the presence of at least 4 of the following findings: 
 * History of appropriate allergen exposure * Restrictive lung function (FVC < 80% predicted for age and FVC/FEV1 < 1) testing, if appropriate for age (usually > 5 y) * Positive serum precipitins for bird/fungus exposed to (other allergens have rarely, if ever been demonstrated in children) * Lymphocytosis in BAL (> 20% of cells are lymphocytes) * HRCT showing the characteristic nodular, linear or reticular opacities and ground glass pattern with increased attenuation. * Lung biopsy demonstrating lymphocytic alveolitis, bronchiolitis, and non-caseating histiocytic granulomas. * Controlled allergen exposure followed by characteristic reaction, including fever, coughing, restriction on lung function, hypoxemia/desaturation at rest or with exercise 2. Unchanged inhaled steroids if on; if off, no plans to introduce them in the following 6 months

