RELEVANCE	
 World-wide the first, randomized controlled trial in children with interstitial lung disease ever and the first clinical project, unifying several pediatric pneumology sites from different European countries into a common project Direct improvement of the health of children with EAA across Europe and wide spread distribution of state of the art protocols to diagnose and treat EAA in childhood. Substantial increased awareness of the child-EU-project in the pediatric pneumology area Strengthened position of the European Pediatric Pneumology within the international Pneumology Scene
STUDY FLOW CHART	
The study flow chart illustrates the study timeline and design. It begins with a 'Run In and Induction treatment' phase from Day -21 (max.) through 0. This is followed by a 'Blinded Intervention' phase from Day 1 through month 3, and a 'Blinded follow up' phase from Month 3 through 6. The 'Blinded Intervention' phase includes 'Tapered oral prednisolone' for the active group and 'Tapered oral placebo' for the control group. The 'Blinded follow up' phase includes a 'Long term follow up' period. The 'Run In and Induction treatment' phase includes 'Screening', 'diagnosis confirmation', 'allergen elimination', and 'hpatient' admissions. The 'Blinded Intervention' phase includes 'Baseline' (3 d with steroid pulses) and 'hpatient' admissions. The 'Blinded follow up' phase includes a 'Long term follow up' period.

Trial schedule

Table 1

Visit	Inpatient	Inpatient	Inpatient	Inpatient	Visit 1	Visit 2 and	Visit 3		Visit 4	Long term follow up
Action	Screening, diagnosis confirmation, allergen elimination	Baseline	Steroid pulse Treatment	Discharge	1 month	Personal contact 2 month	3 month		6 month	annually
Trial day	-21 to -2	-4 to -2	-2 to 0	1	28 (21, 35)	56 (49, 63)	84 (74, 94)		168 (148, 188)	annually
Demographics (sex, age, race)	X									
Patient information, informed consent	X									
Previous and concomitant diseases	X					X				X
Previous and concomitant treatments	X					X				X
Inclusion/exclusion criteria	X									
Randomization ^a	X									
Medication supply					X					
Expert allergen consultation and education ^b	X (in hospital)						X (at home)			
Physical examination	X					X	X			
Pregnancy test ^k	X								X	
Vital signs (Height, weight, BP, pulse, temp) ^c	X					X	X			
Blood sample ^d				X						
FVC % predicted (spirometry) ^e	X*	X			X	X	X	X		X X

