4.4 Open rescue treatment if lung function does not improve

With removal of the allergen by hospitalization and cleaning of the home from offending allergens which is usually done during the initial hospital stay, and after application of the 3d steroid boost to all subjects, a steady improvement in lung function is anticipated. This will be closely monitored by monthly lung function measurements in the first 3 months and at 6 months or additional visits at the discretion of the treating physician. FVC (% predicted) is expected to increase from visit to visit.

If this is not the case, continuing allergen exposure must be considered and a re-evaluation of the allergen elimination has to be performed.

If there is no appropriate improvement of lung function despite appropriate allergen elimination, an open rescue treatment with oral prednisolone (0.5 mg/kg bw/d) should be given till the patient's lung function improves. An alternative may be pulsed methylprednisolone (10 mg/kg bw/d). Extra visits at the discretion of the treating physician may be scheduled.

If the result of the oral prednisolone is not satisfying, re-evaluation of the diagnosis and possibly de-blinding of the study medication should be considered. Alternative medication, including steroid sparing drugs may be considered.

All rescue treatments necessary will be recorded and the cumulative amount of steroids necessary used as a secondary outcome variable.

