6. TRIAL METHODS

6.1 Assessment of efficacy

The primary analysis variable is the improvement in FVC (difference after 6 months and baseline). The 6 months and baseline FVC values will be given in percent deviation from the norm values tabulated by Quanjer PH., et al. 2013. FVC will be measured by performing a standardized spirometry with defined quality criteria according to the ATS/ERS guideline. Therefore a standard operation procedure will be provided.

For the evaluation of the quality of life a standardized questionnaire, the “PedsQL”, will be used.

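### The restrictive lung function finding uses FVC/FEV1 < 1 without a stated scale: it cannot be met in measured volumes but can be met in % predicted, so the same spirometry can be scored either way

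*Protocol*

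**What the plan says.** Protocol section 3.6.1 requires that the diagnosis be confirmed by an expert panel, and it "must be based on the presence of at least 4 of the following findings". Seven findings follow. The second is "Restrictive lung function (FVC < 80% predicted for age and FVC/FEV1 < 1) testing", to be used where the patient's age allows it. The key inclusion criteria in the synopsis use the same condition, "FVC < 80% predicted for age and FVC/FEV1 < 1", so this is not a slip in one place only.

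The two parts are joined by *and*. The first is in % predicted. The second is a bare ratio with no scale.

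Elsewhere the protocol treats FVC relative to norm values:
- Table 1 lists "FVC % predicted (spirometry").
- Section 4.4 says "FVC (% predicted) is expected to increase from visit to visit".
- Section 6.1 says "The 6 months and baseline FVC values will be given in percent deviation from the norm values tabulated by Quanjer PH., et al. 2013".

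No section shown puts FEV1 on such a scale. Outside the entry criterion, FEV1 appears only in section 1.3, in the account of earlier studies.

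**The concern.** A ratio of two spirometric volumes with no qualifier is ordinarily read as a ratio of the measured values. Read that way, the second condition is impossible. Because of the *and*, the whole finding would then fail for every patient, including one at the mean FVC of 39% of predicted that section 1.3 reports for the sponsor's own series.

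What is at stake is consistent eligibility scoring. Restrictive lung function is one of seven findings of which four are needed, so for some patients it decides entry. A site or panel member who takes the ratio in litres never counts it. One who takes it in % predicted counts it for some patients with reduced FVC and not for others. The protocol expects more than 40 centres (section 3.2), and each decides which patients to put forward.

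**Working it through.** The protocol gives no figure to reproduce here. The check is whether the condition can be met on each plausible scale, and what follows if it cannot.

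**1. Measured volumes.** FEV1 is the part of the forced expiration exhaled in the first second, so FEV1 ≤ FVC and FVC/FEV1 ≥ 1. A child who empties completely within one second gives exactly 1, which still fails < 1. Taking the best FVC and the best FEV1 from different blows does not help: the largest FVC is at least the FVC of the blow with the best FEV1, which is at least that FEV1. In 200,000 simulated best-of-three sets the smallest ratio was 1.0000007.

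**2. Both values in % predicted.** The ratio is

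(FVC / predicted FVC) ÷ (FEV1 / predicted FEV1) = (predicted FEV1/FVC) ÷ (observed FEV1/FVC).

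It is below 1 exactly when observed FEV1/FVC exceeds its predicted value. The protocol gives no predicted FEV1/FVC, so a range of 0.85 to 0.90 is assumed:

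| Predicted FEV1/FVC (assumed) | Observed 0.85 | Observed 0.88 | Observed 0.90 | Observed 0.95 |
|---|---|---|---|---|
| 0.85 | 1.000, not met | 0.966, met | 0.944, met | 0.895, met |
| 0.88 | 1.035, not met | 1.000, not met | 0.978, met | 0.926, met |
| 0.90 | 1.059, not met | 1.023, not met | 1.000, not met | 0.947, met |

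On this scale the condition can be met, and it separates patients.

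**3. Ratio written upside down.** If FEV1/FVC < 1 in measured volumes was intended, almost everyone would meet it and it would not identify restriction. Swapping the terms alone is therefore no repair.

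**4. One patient, three scores.** Take FVC at 60% predicted and an assumed predicted FEV1/FVC of 0.88.

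| Observed FEV1/FVC | Measured volumes | % predicted | Inverted ratio, measured volumes |
|---|---|---|---|
| 0.95 | not met | met (0.926) | met |
| 0.85 | not met | not met (1.035) | met |

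**5. Effect on the counting rule if the finding is lost.**
- At least 4 of 7: 35 + 21 + 7 + 1 = 64 of 128 possible patterns of findings qualify.
- At least 4 of 6: 15 + 6 + 1 = 22 of 64 qualify.

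These count patterns; they are not probabilities, because the findings are neither equally common nor independent. They show that entry would be harder but still possible.

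**The case against.** The strongest reply is that litres are nowhere stated. The same parenthesis gives FVC in % predicted, and the schedule, the rescue section and the endpoint definition all use norm-referenced FVC. On that scale the ratio is sensible: FVC is reduced more than FEV1, which distinguishes restriction from obstruction. This stands as far as it goes. It shows that a workable reading exists and may be what was meant. It does not settle the matter, because % predicted is attached only to the first condition and FEV1 is never put on that scale. A spirometry SOP is promised and is not at hand. It might help sites, but the entry criterion itself should be clear.

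The second reply is that an independent expert panel confirms every diagnosis, so site readings alone do not decide enrolment. This also stands, and it narrows the problem. It does not remove it: the panel works from the same sentence, and sites apply it first when choosing whom to submit.

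A reader might infer more than the documents support:
- **That the finding is unusable, or never met.** This is true only for measured volumes, a scale the protocol does not state.
- **That every patient would need lavage, biopsy or an exposure test.** History, precipitins, HRCT and lung function are the four findings that need none of these, so losing lung function would leave three. But that grouping is not the protocol's, the inference again assumes measured volumes, and section 1.1 already names lavage among the ordinary bases of diagnosis.
- **That eligible patients will be refused.** This is a possibility; nothing in the protocol shows it.

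**Conclusion.** The concern holds as an ambiguity in an eligibility criterion. The scale of FVC/FEV1 is not stated in section 3.6.1 or in the synopsis. In measured volumes the condition is impossible, and the rule is in effect 4 of 6. In % predicted it can be met whenever observed FEV1/FVC exceeds its predicted value. The text does not choose between these readings.

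The impossibility in measured volumes follows from the definition of FEV1 and needs no assumption. The numerical examples in % predicted rest on the assumed predicted FEV1/FVC of 0.85 to 0.90; the direction of the result does not.

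Severity is low to moderate. No single finding is mandatory, any four of the other six suffice, and the panel limits variation between readers. The ratio enters neither the 58% power in section 7.1 nor the ANCOVA in section 7.3.1.

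**What to change.** In section 3.6.1 and in the synopsis, the sponsor should state the scale and the direction of the ratio so that the condition can be met and identifies restriction. If a ratio of % predicted values was meant, it is enough to say that both FVC and FEV1 are in % predicted. If something else was meant, write the ratio with its scale, direction and cut-off. Give sites and the expert panel that same wording.

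The cost is one line in two places. No new data are needed, and the sample size and analysis do not change. The correction belongs in the protocol because it concerns an inclusion criterion.
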